2.1 Objectives & Hypotheses

Primary

To determine the absolute and relative effects at Tmax of Belsomra 10 mg; 20 mg; and placebo on responsiveness in nonelderly insomniacs (< 65 yrs).

We hypothesize that:

- 1) Belsomra 20 mg will have a similar awakening/arousal threshold compared to placebo
- 2) Belsomra 10 mg will have a similar awakening/arousal threshold compared to placebo
- 3) Belsomra 20 mg will have a similar awakening/arousal threshold to Belsomra 10 mg

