
2.3 Study Design
	
The proposal is for an interventional single site study using a double blind, randomized 3-way crossover design with Belsomra 10 mg and 20 mg compared to a placebo. The total number of enrolled patients proposed is 12 providing reasonable power (>70%) to detect differences of 15 db vs. placebo for Belsomra if present (although no differences are expected). Patients will be crossed over to experience all treatment conditions in a controlled order (Belsomra 10 mg, 20 mg and placebo). Both men and women with insomnia will be utilized as the study population to improve the generalizability of outcome data. However, we will enroll equal numbers of men and women in order to allow comparative analyses within both men and women, albeit with reduced power. In the overall analyses sex will be utilized as a covariate. Subjects with other sleep disorders or unstable medical/psychiatric disorders will be excluded from the trial. Inclusion criteria will be men and women >18 and < 65 years of age.
 
An initial standardized screening PSG will be used to rule out the presence of sleep disordered breathing and/or periodic limb movements during sleep (mean AHI/PLMAI <10/hr for both). The 3 study treatments include Belsomra 10 mg and 20 mg with a middle-of-the-night awakening at ~2.5 hours (BEL10; BEL20), and placebo with a middle-of-the-night awakening at 2.5 hours (PBO). Study drug will be administered under fasted conditions (at least 3 hours) as a single dose at bedtime (approximately 2300 hours), and each subject will receive one dose of each active drug, and one dose of placebo during the treatment period for a total of 3 overnight testing sessions and 1 overnight PSG screening.
 
Subjects will be randomly assigned to treatment sequences using a Latin square design. After a subject has qualified for the study, the next sequentially available randomization number will be assigned. The subject will be administered study drug corresponding with this assigned number.
 
Inclusion Criteria:
 
 • Meets DSM-5 diagnostic criteria for insomnia disorder • ISI > 10 • Age >18 and < 65 • Negative audiological screening exam 
Exclusion Criteria:

- BMI >35 kg/m²
- Have symptoms consistent with the diagnosis of any sleep disorder other than insomnia (e.g., sleep apnea, narcolepsy, periodic leg movements, or restless leg syndrome).

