
2.6 Study Duration
	
The expected duration of study participation for a patient is ~30 days, including up to 14 days for medical screening, and 3 one-night treatments. All assessments will be separated by a 6-12 day drug free interval. A maximum of 3-4 patients will be enrolled in the study at a given time. Thus, the expected duration for study completion will be ~9 months.

2.7 Statistical Analysis and Sample Size Justification
	
The Sleep Disorders Center will be responsible for analyzing the study data (Investigator and expert statistical staff). The blind will be maintained during the study and the data will be unblinded at the completion of the trial. For the purpose of the final analysis, the official clinical database will not be unblinded until medical/scientific review has been completed, protocol violations have

been identified and data has been declared complete in conjunction with the study Sponsor.

Data analysis will compare the change from placebo in each active drug condition. The primary analysis will be based on the evaluable population, defined as subjects who have data from each of the three Treatment Periods with no major protocol violations. Safety analyses will be presented descriptively for the safety population; defined as all subjects who were randomized and received at least one dose of study medication.

The primary endpoint will be the mean Auditory Arousal Threshold in decibels (AAT).

All statistical analyses will be conducted using IBM SPSS Statistics for Windows – Version 23 (Armonk, NY). The primary outcome of the study include within-person differences between active medications and respective placebo on the AAT. Univariate within-group comparisons for these continuous endpoints will be accomplished via paired samples t-tests. Repeated-measures analysis of covariance (ANCOVA) analyses will be used for estimating more complex models involving multiple factors or covariates (e.g., age. Given the extensive array of variables, covariates will be selected for inclusion in omnibus models per recommendations outlined by Mickey and Greenland (1989). Specifically, only those variables are related to the dependent variable in univariate analyses at a significance level of $P < 0.20$ will be retained in the final model. Similar analyses will be used to examine all potential secondary/exploratory endpoints.

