Power analyses: Based on a previous study using zolpidem 10 mg in younger men, we estimate the power for this project to be 70% or greater for detecting a mean difference of ~15 db between belsomra and placebo given a sample of 12 individuals. This assumes a variance of 15 db. In our previous study the variance was ~15 db indicating an effect size of $d=1.0$. We do not expect insomnia status to impact the arousal threshold effect size as shown in previous studies (Johnson et al., 1978).

Safety and tolerability will be assessed by statistical and clinical review of the data on adverse clinical events, such as complex sleep-related behaviors, predefined limits of change for selected laboratory and vital sign values, as well as next-day residual effects. The primary approach for all safety analyses will be the All Patients as Treated (APaT) approach. All randomized patients who receive at least one dose of study medication will be included in the safety analyses.

The results will be reported using summary tables, figures, and data listings. Continuous variables will be summarized using mean, standard deviation, median, minimum, and maximum values. Categorical variables will be summarized by presenting the number (frequency) and percentage in each category.

	
Demographics will be tabulated and summarized. Medical history data at Screening will be listed, as will Physical Examination data including height and weight. Vital signs (resting heart rate, systolic/diastolic blood pressure, respiratory rate and temperature) will be tabulated and summarized.
 
Treatment-emergent adverse events will be listed and summarized. Adverse events reported in this study will be coded using MedDRA (Medical Dictionary for Regulatory Activities).
 
Clinical laboratory data will be summarized with descriptive statistics. Abnormal laboratory test results will be flagged in the subject data listings.

2.8 Specific Drug Supply Requirements
	
Suvorexant will be supplied by Merck. Due to the limited nature of study drug needed the HFHS pharmacy will not require bulk supplies (if necessary study drug can be purchased by HFHS pharmacy and over encapsulated for the study procedures in house). Study drug will be unknown to the patient and therefore will be labeled only with study night number.

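### The three primary hypotheses claim a similar arousal threshold, but the planned test and the sample size address only a difference, and no margin or interval rule can support similarity

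*Protocol*

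**What the plan says.** Section 2.1 of the protocol lists three primary hypotheses, all of the same kind. The first is that "Belsomra 20 mg will have a similar awakening/arousal threshold compared to placebo". The second says the same of 10 mg, and the third is that "Belsomra 20 mg will have a similar awakening/arousal threshold to Belsomra 10 mg". None comes with a margin.

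Section 2.7 sets out the analysis: "Data analysis will compare the change from placebo in each active drug condition". It continues: "The primary outcome of the study include within-person differences between active medications and respective placebo on the AAT". The method is then named: "Univariate within-group comparisons for these continuous endpoints will be accomplished via paired samples t-tests". Repeated-measures ANCOVA is kept for models with several factors or covariates.

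The sample size of 12 is justified in two places. Section 2.3 speaks of "reasonable power (>70%) to detect differences of 15 db vs. placebo for Belsomra if present (although no differences are expected". Section 2.7 says "we estimate the power for this project to be 70% or greater for detecting a mean difference of ~15 db between belsomra and placebo", taking a variability of 15 dB and hence a standardised effect of 1.0.

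The protocol contains no equivalence or non-inferiority test, no similarity margin, and no rule for reading a confidence interval.

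**The concern.** A paired t-test asks whether the mean difference is zero. Rejecting zero would count against hypothesis 1 or 2. Failing to reject supports nothing, because with 12 patients a non-significant result is compatible with no effect and also with a sizeable rise in threshold. The protocol does not say that a non-significant test will be read as similarity, but it offers no other route to the conclusion it predicts.

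The investigators expect no difference, so a non-significant result is the likely outcome and its interpretation matters. Section 2.2 treats being able to respond to a stimulus at night as a safety matter, so an unsupported claim of similarity would be false reassurance on a safety-relevant endpoint.

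There is also a gap in the contrasts. Section 2.7 words the comparison only as active drug against placebo, so the 20 mg versus 10 mg contrast that hypothesis 3 needs is not named.

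**Working it through.** **Inputs.** From the protocol: n = 12, crossover, paired comparison; detectable difference 15 dB; standardised effect 1.0, so the variability of 15 dB is read as an SD. Assumed because not stated: two-sided alpha of 0.05; 15 dB as the SD of the paired difference; 12 patients with complete data.

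**1. The plan's own power figure.** Noncentrality = (15/15) × √12 = 3.46, df = 11, critical t = 2.201. Power is 88%, consistent with the stated 70% or greater. The SD that brings power for 15 dB down to exactly 70% is 19.05 dB. It serves below as a second scenario. If 15 dB were the SD per condition with zero within-person correlation, the paired SD would be 15 × √2 = 21.2 dB and power 61%, so 19.05 dB is not a worst case.

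**2. What a non-significant result leaves open.** Probability of non-significance = 1 − power from the noncentral t; 95% CI half-width = 2.201 × SD/√12.

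| Paired SD | True rise 5 dB | 10 dB | 15 dB | 95% CI half-width |
|---|---|---|---|---|
| 15 dB | 82% | 44% | 12% | 9.5 dB |
| 19.05 dB | 87% | 62% | 30% | 12.1 dB |

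With an observed SD of 15 dB, a mean rise is non-significant if it is below 9.53 dB. Its 95% CI includes 15 dB if it is above 15 − 9.53 = 5.47 dB. Any observed mean rise between about 5.5 and 9.5 dB is therefore non-significant and still compatible with the very difference the trial is sized to detect. The upper limit can reach 9.53 + 9.53 = 19.1 dB.

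**3. Power to conclude similarity, if a margin existed.** The rule is two one-sided tests at 0.05 each (TOST), that is, the 90% CI must lie inside ± margin. True differences are set to 0. Per-comparison power comes from numerical integration over the sample SD. Power for all three comparisons comes from simulation with equal paired SDs. The margins are illustrative, because the protocol gives none.

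| Margin | SD 15: each | SD 15: all three | SD 19.05: each | SD 19.05: all three |
|---|---|---|---|---|
| 15 dB | 89% | 75% | 64% | 35% |
| 13.5 dB | 80% | 58% | 49% | 20% |
| 10 dB | 41% | 13% | 14% | 1% |

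Power of 80% per comparison is reached at a margin of 13.5 dB with SD 15 and 17.2 dB with SD 19.05. Whether 12 patients are enough thus depends entirely on a margin the protocol does not state.

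**The case against.** The strongest defence is that the primary objective is worded as determining absolute and relative effects, which is estimation. On that reading the hypotheses only state an expectation, and a paired analysis yields an estimate and a confidence interval anyway. It is true that the data can support an interval-based conclusion. But section 2.7 names t-tests as the inference, the hypotheses assert similarity, and no rule turns an interval into that assertion.

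A second point is that the troublesome result is not common if the drug truly has no effect. With SD 15 and a true difference of 0, about 10% of trials would be non-significant with a 95% CI reaching +15 dB; with SD 19.05 it is about 28%. This stands as context. It does not help with true rises of 5 to 10 dB, which would often be missed, and the protocol does not say which rises matter.

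Third, the safety worry runs in one direction, so a one-sided upper-limit rule could be used in place of TOST. At a 10 dB margin and SD 15 it gives 56% power at one-sided 0.025, against 41%. That is a legitimate variant, but it too needs a margin and a different hypothesis wording. Likewise, power for all three comparisons matters only if a joint claim is made.

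Finally, a SAP might add a margin and name the 20 mg versus 10 mg contrast, and the repeated-measures model could carry that contrast. Even so, the hypotheses, the test and the basis for 12 patients are all fixed in this protocol and do not fit together. A margin added elsewhere would leave the sample size justified for a different question.

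**Conclusion.** The protocol is wrong as written on this point, and the defect affects all three primary hypotheses. The planned tests can contradict the similarity of each dose to placebo but cannot establish it, and the 20 mg versus 10 mg comparison is not named in the analysis section. Under the assumptions above, a true 10 dB rise would go undetected in 44% (SD 15) to 62% (SD 19.05) of trials. Twelve patients are not shown to be too few: at SD 15 they give 89% TOST power per comparison for a 15 dB margin, but only 41% for 10 dB. What is missing is the margin or interval rule, and the power for it. Correction is needed before unblinding, because a margin chosen after seeing the data would not be credible.

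**What to change.** In section 2.7, make the mean paired difference with its 95% CI the basis of inference for all three contrasts, naming 20 mg versus 10 mg. State that a non-significant t-test or ANCOVA term is not evidence of similarity. Then choose one of two routes.

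- **Similarity claim.** Pre-state a justified margin, conclude similarity only if the 90% CI lies within it (TOST, 0.05 each side), and restate the power for that rule per comparison and, if a joint claim is intended, for all three. A margin of 15 dB would need its own justification, since it is the difference the trial is sized to detect.
- **Estimation.** If no margin that 12 completers can support is justifiable, reword the hypotheses in section 2.1 as estimation with 95% CIs, in line with the stated objective, and make no similarity claim.

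The cost is wording in sections 2.1 and 2.7 and a recomputed power statement, with no extra patients, visits or budget. The price is that similarity cannot be claimed from a wide interval, and the restated power may look less favourable: 41% per comparison at a 10 dB margin with SD 15, or 64% at 15 dB with SD 19.05.

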2.2 Background & Rationale, Significance of Selected Topic & Preliminary Data

Insomnia is characterized by difficulty falling asleep, waking frequently during the night, waking too early in the morning and not being able to get back to sleep, and waking feeling unrefreshed. Insomnia can be transient (lasting for several days), intermittent (when transient insomnia recurs), or chronic (lasting for more than a month and has been reported in all age groups. An estimated 30%-50% of the adult population is affected by insomnia and prevalence tends to increase with age.

Hypnotic medications are utilized to improve sleep initiation and/or maintenance. The most commonly used hypnotics, Benzodiazepine Receptor Agonists (BzRAs), bind at the benzodiazepine receptor at the GABA-A complex and demonstrate broad CNS depressant effects which been shown to reduce responsiveness to the environment, particularly at peak plasma concentrations (Frey, et al., 2011; Zammit et al., 2008). The ability to respond following a nocturnal stimuli is critical to safety (e.g., responding to fire alarms, infants, burglary, or other emergencies) (Johnson et al., 1983). Recently, the hypnotic suvorexant (dual orexin antagonist) has been shown to have no effects on the ability to wake to a novel auditory stimuli and thus may have a comparative benefit to BzRA hypnotics in terms of auditory awakening threshold (Tannenbaum et al., 2014; 2016). However, the previous study was not done in humans. The present study is designed to test arousal response (responsivity) at peak plasma levels following administration of Belsomra (10 and 20 mg) compared to placebo. Specifically, responsiveness will be assessed using standardized measures as in a previous study of auditory awakening threshold (Drake et al., 2017). The doses proposed are Belsomra 10 mg and 20 mg as these represent the clinically recommended and utilized doses.

The Primary objective is to determine the absolute and relative effects of Belsomra 10 mg and 20 mg on responsiveness during sleep in patients with insomnia at estimated Tmax versus placebo (~2.5 hrs post-dosing).

	
Our Sleep Research Center has considerable experience in the design and execution of responsivity studies. In a recent trial published in 2017 we compared the effects of a 10 mg dose of zolpidem to placebo in men to determine the level of responsivity and balance/Ataxia effects at T-max (~2.5 hrs.). Results of this trial showed a significantly higher auditory awakening threshold for zolpidem compared to placebo ($p < .001$). In addition, the effects of zolpidem on middle of the night balance were also significantly greater than placebo ($p < .005$). We expect a similar effect size in the present study as compared to what was found for placebo in our previous trial.


2.3 Study Design
	
The proposal is for an interventional single site study using a double blind, randomized 3-way crossover design with Belsomra 10 mg and 20 mg compared to a placebo. The total number of enrolled patients proposed is 12 providing reasonable power (>70%) to detect differences of 15 db vs. placebo for Belsomra if present (although no differences are expected). Patients will be crossed over to experience all treatment conditions in a controlled order (Belsomra 10 mg, 20 mg and placebo). Both men and women with insomnia will be utilized as the study population to improve the generalizability of outcome data. However, we will enroll equal numbers of men and women in order to allow comparative analyses within both men and women, albeit with reduced power. In the overall analyses sex will be utilized as a covariate. Subjects with other sleep disorders or unstable medical/psychiatric disorders will be excluded from the trial. Inclusion criteria will be men and women >18 and < 65 years of age.
 
An initial standardized screening PSG will be used to rule out the presence of sleep disordered breathing and/or periodic limb movements during sleep (mean AHI/PLMAI <10/hr for both). The 3 study treatments include Belsomra 10 mg and 20 mg with a middle-of-the-night awakening at ~2.5 hours (BEL10; BEL20), and placebo with a middle-of-the-night awakening at 2.5 hours (PBO). Study drug will be administered under fasted conditions (at least 3 hours) as a single dose at bedtime (approximately 2300 hours), and each subject will receive one dose of each active drug, and one dose of placebo during the treatment period for a total of 3 overnight testing sessions and 1 overnight PSG screening.
 
Subjects will be randomly assigned to treatment sequences using a Latin square design. After a subject has qualified for the study, the next sequentially available randomization number will be assigned. The subject will be administered study drug corresponding with this assigned number.
 
Inclusion Criteria:
 
 • Meets DSM-5 diagnostic criteria for insomnia disorder • ISI > 10 • Age >18 and < 65 • Negative audiological screening exam 
Exclusion Criteria:

- BMI >35 kg/m²
- Have symptoms consistent with the diagnosis of any sleep disorder other than insomnia (e.g., sleep apnea, narcolepsy, periodic leg movements, or restless leg syndrome).
- Have a known or suspected diagnosis of Acquired Immune Deficiency Syndrome (AIDS), or have tested seropositive for human immunodeficiency virus (HIV) antibody or antigen previously.
- Have any clinically significant abnormal finding in physical examination, neurological assessment, vital signs, elevated body temperature, or clinical laboratory tests, as determined by the Investigator.
- Have a known or exaggerated pharmacological sensitivity, hypersensitivity, or intolerance to Belsomra.
- Currently taking CYP3A inhibitors.
- Positive breathalyzer test for alcohol at Screening, PSG Screening or any Treatment night, or a positive urine drug screen (for amphetamines, barbiturates, benzodiazepines, cocaine, opiates, or cannabinoids) at Screening;
- History of hearing difficulty (e.g., use of a hearing aid).
- Intends to use any medication including over-the-counter (OTC) medications that would interfere with normal sleep architecture (such as systemic steroids, beta-adrenergic blockers, amphetamines, modafinil, etc.);
- Self-reports use of products containing nicotine of greater than 15 cigarettes daily, or cannot avoid products containing nicotine during the normal sleep periods;
- Self-report consumption of more than five alcoholic beverages on any one day or > 14 alcoholic beverages weekly over the past week;
- Have a history of epilepsy or serious head injury
- Average TIB < 6.5 hrs.
- Have used prescribed or OTC medications within 7 days of screening (Day 0) or intend to use any prescription or OTC medication during the study that may interfere with the evaluation of the study drug. This restriction includes taking medications that affect the CNS. Any chronic maintenance therapy should have been maintained at a stable dosing regimen for at least 30 days before screening and subjects must continue this regimen throughout the study.
- Have used an investigational drug within 30 days or five half-lives (whichever is longer) before screening, or plans to use an investigational drug during the study or have used BEL/ZOL.

A study timeline is included below:

Evaluation Timing	Screening Period Days -14 to -1	Crossover Treatment Period			
		TX 1	TX 2	TX 3	Final Study Day
Informed Consent	X				
Inclusion/Exclusion	X				
Breathalyzer Test	X	X	X	X	
Urine Drug Screen	X				
Medical History	X				
Sleep Heart Health Survey	X				
Epworth Sleepiness Scale	X				
Restless Leg Questionnaire	X				
Stop Bang Questionnaire	X				
Laboratory (Routine)	X				
Vital Signs	X	X	X	X	X
Physical Examination	X				X
Randomization	X				
Height, Weight, BMI	X				
Prior & Concomitant Medications	X	X	X	X	X
Study Drug Administration		X	X	X	
AAT		X	X	X	
PSG	X	X	X	X	
Adverse Events		X	X	X	X

2.5 Study Procedures
	
Subjects will be screened by clinical interview and full physical evaluation to establish health, and rule out medical disorders and sleep disorders other than insomnia. In addition, participants will complete medical history and be asked to complete a Sleep Health Survey and sleep disorders questionnaires to rule out restless leg syndrome and sleep disordered breathing (RLS screening questionnaire and STOP-BANG questionnaire). Participants will be screened using standard urine and blood chemistry laboratory tests (LabCorps) and be administered a breathalyzer to screen for alcohol and urine drug screen. AAT protocol will be reviewed and demonstrated with each participant on the morning of the screening PSG.
 
During the night of each respective PSG assessment night, subjects will be awoken at the approximate T-max of the active drug (2.5 hrs), with a matching placebo condition at the same time point using an identical responsivity protocol for each condition. The rationale for this is that t-max represents the time of greatest potential risk for a hypnotic in terms of balance, responsivity, and memory. Responsivity will be assessed using the Auditory Awakening Threshold test (AAT) and will be measured at 2.5 hours post dose for the Belsomra 10 and 20 mg (BEL), and placebo (PBO) conditions. Responsivity will be assessed at the approximate time above immediately after 5 minutes of consolidated (without arousals) NREM stage 2 sleep has occurred.
 
Responsivity Protocol: Responsivity will be measured in response to a series (20-sec intervals) of increasing 1.5-sec. tones at 520 Hz (fire alarm) with a range from 40 db to 110 db. The outcome measure will be the mean decibel level (db) at awakening (mean of 2 awakenings at ~T-max for each subject for each condition).
 
Subjects will be discharged from the sleep center once all assessments have been completed. A 6-12 day drug-free interval will separate each Treatment Period. A final study visit will be performed for subjects either after they have completed all three Treatment Periods or they have prematurely discontinued the study.


2.6 Study Duration
	
The expected duration of study participation for a patient is ~30 days, including up to 14 days for medical screening, and 3 one-night treatments. All assessments will be separated by a 6-12 day drug free interval. A maximum of 3-4 patients will be enrolled in the study at a given time. Thus, the expected duration for study completion will be ~9 months.

2.7 Statistical Analysis and Sample Size Justification
	
The Sleep Disorders Center will be responsible for analyzing the study data (Investigator and expert statistical staff). The blind will be maintained during the study and the data will be unblinded at the completion of the trial. For the purpose of the final analysis, the official clinical database will not be unblinded until medical/scientific review has been completed, protocol violations have

been identified and data has been declared complete in conjunction with the study Sponsor.

Data analysis will compare the change from placebo in each active drug condition. The primary analysis will be based on the evaluable population, defined as subjects who have data from each of the three Treatment Periods with no major protocol violations. Safety analyses will be presented descriptively for the safety population; defined as all subjects who were randomized and received at least one dose of study medication.

The primary endpoint will be the mean Auditory Arousal Threshold in decibels (AAT).

All statistical analyses will be conducted using IBM SPSS Statistics for Windows – Version 23 (Armonk, NY). The primary outcome of the study include within-person differences between active medications and respective placebo on the AAT. Univariate within-group comparisons for these continuous endpoints will be accomplished via paired samples t-tests. Repeated-measures analysis of covariance (ANCOVA) analyses will be used for estimating more complex models involving multiple factors or covariates (e.g., age. Given the extensive array of variables, covariates will be selected for inclusion in omnibus models per recommendations outlined by Mickey and Greenland (1989). Specifically, only those variables are related to the dependent variable in univariate analyses at a significance level of $P < 0.20$ will be retained in the final model. Similar analyses will be used to examine all potential secondary/exploratory endpoints.

Power analyses: Based on a previous study using zolpidem 10 mg in younger men, we estimate the power for this project to be 70% or greater for detecting a mean difference of ~15 db between belsomra and placebo given a sample of 12 individuals. This assumes a variance of 15 db. In our previous study the variance was ~15 db indicating an effect size of $d=1.0$. We do not expect insomnia status to impact the arousal threshold effect size as shown in previous studies (Johnson et al., 1978).

Safety and tolerability will be assessed by statistical and clinical review of the data on adverse clinical events, such as complex sleep-related behaviors, predefined limits of change for selected laboratory and vital sign values, as well as next-day residual effects. The primary approach for all safety analyses will be the All Patients as Treated (APaT) approach. All randomized patients who receive at least one dose of study medication will be included in the safety analyses.

The results will be reported using summary tables, figures, and data listings. Continuous variables will be summarized using mean, standard deviation, median, minimum, and maximum values. Categorical variables will be summarized by presenting the number (frequency) and percentage in each category.

	
Demographics will be tabulated and summarized. Medical history data at Screening will be listed, as will Physical Examination data including height and weight. Vital signs (resting heart rate, systolic/diastolic blood pressure, respiratory rate and temperature) will be tabulated and summarized.
 
Treatment-emergent adverse events will be listed and summarized. Adverse events reported in this study will be coded using MedDRA (Medical Dictionary for Regulatory Activities).
 
Clinical laboratory data will be summarized with descriptive statistics. Abnormal laboratory test results will be flagged in the subject data listings.

2.8 Specific Drug Supply Requirements
	
Suvorexant will be supplied by Merck. Due to the limited nature of study drug needed the HFHS pharmacy will not require bulk supplies (if necessary study drug can be purchased by HFHS pharmacy and over encapsulated for the study procedures in house). Study drug will be unknown to the patient and therefore will be labeled only with study night number.

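### The primary AAT comparison uses paired t-tests with no period term, although treatment order is randomised by Latin square over three nights

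*Protocol*

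**What the plan says.** Section 2.3 describes a three-way crossover (10 mg, 20 mg, placebo) in 12 patients: "Subjects will be randomly assigned to treatment sequences using a Latin square design". Section 2.5 spaces the nights: "A 6-12 day drug-free interval will separate each Treatment Period".

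Section 2.7 names the primary contrast, "The primary outcome of the study include within-person differences between active medications and respective placebo on the AAT", and the test for it: "Univariate within-group comparisons for these continuous endpoints will be accomplished via paired samples t-tests". A second method is named for other purposes: "Repeated-measures analysis of covariance (ANCOVA) analyses will be used for estimating more complex models involving multiple factors or covariates". Its example covariate is age, and Section 2.3 adds sex. Other covariates face a screen: "only those variables are related to the dependent variable in univariate analyses at a significance level of" P < 0.20 are kept. Period, night, order and sequence appear in no analysis sentence.

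The analysis set is restricted: "The primary analysis will be based on the evaluable population, defined as subjects who have data from each of the three Treatment Periods" and who have no major violations. One listed exclusion can arise after randomisation: "Positive breathalyzer test for alcohol at Screening, PSG Screening or any Treatment night".

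**The concern.** The Latin square balances treatments over nights so that a night effect can be separated from the treatment effect and removed from the error. The paired t-test makes only half of that use. Balance cancels a common night effect from the mean difference, but the effect stays in the spread of the individual differences, because patients took the two treatments on different pairs of nights. The t-test treats that spread as noise.

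A night effect is plausible. The AAT is demonstrated on the morning of the screening PSG (Section 2.5), but the study timeline shows it performed only on the three treatment nights, so the first treatment night is also the first overnight exposure to the tones.

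With 12 patients, precision is the limiting factor. The hypotheses in Section 2.1 are of similarity, and no margin is stated. If a non-significant difference is read as similarity, a conservative test makes that result easier to reach. If similarity is judged by confidence intervals, wider intervals make it harder to show. Neither is wanted.

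**Working it through.** **Inputs.** N = 12, target difference 15 dB and power of 70% or more come from Sections 2.3 and 2.7. Section 2.7 gives a variance of 15 dB and d = 1.0. Since 15/15 = 1.0, the 15 dB is read as an SD and, by assumption, as the SD of the paired differences. Alpha 0.05 two-sided is assumed. The protocol gives no night effect, so a linear drift of 0 to 10 dB per night is assumed. The total change from night 1 to night 3 is twice the nightly figure.

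**The plan's own figure.** For a paired t-test with n = 12 and d = 1.0, the noncentrality is √12 × 1.0 = 3.46 and power is 88.3%. This satisfies the stated 70% or more. It allows for no period variance.

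**What drift does to the SD.** With three orders of four patients, the night differences for any one contrast are +1, +1 and −2 (or the reverse). Their mean is 0, so there is no bias. Their sum of squares is 4 × (1 + 1 + 4) = 24, which adds step² × 24/11 to the sample variance of the differences:

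SD = √(225 + step² × 24/11)

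This gives 15.6, 16.7 and 21.1 dB at 3, 5 and 10 dB per night. Six orders of two patients give the same sum of squares, so the number of orders, which the protocol does not state, does not matter here.

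**Simulation.** 20,000 trials per setting, three orders, within-person SD 15/√2. The pairwise contrast adjusts each patient's paired difference for period (12 − 3 = 9 df). The pooled model has patient, period and treatment (36 − 1 − 11 − 2 − 2 = 20 df).

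| Drift, dB per night | 0 | 3 | 5 | 10 |
|---|---|---|---|---|
| Power, paired t (11 df) | 88% | 86% | 83% | 65% |
| Power, period-adjusted pairwise | 87% | 87% | 87% | 87% |
| Power, pooled model | 91% | 91% | 91% | 91% |
| Mean 95% CI half-width, paired t (dB) | 9.3 | 9.7 | 10.4 | 13.1 |
| Type I error of nominal 5% paired t | 5.0% | 4.3% | 3.3% | 0.8% |

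The mean half-width is about 9.5 dB for the period-adjusted pairwise contrast and 8.9 dB for the pooled model at every drift. Paired-t power is 73% at 8 dB per night and 70% at 9. Six orders gave paired-t power within half a point of the table. At zero drift the pooled model's advantage comes from its 20 error df, not from the period term.

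**Sensitivity.**
- A shift confined to the first night costs less: paired-t power is about 87% for 5 dB and 81% for 10 dB.
- If 15 dB is instead the SD within each condition, the SD of differences is 15 × √(2(1 − r)): 11.6 dB at r = 0.7 and 17.7 dB at r = 0.3. At 5 dB per night, paired t against pooled model is then 96% against 99%, or 71% against 80%.
- If the cited 15 dB already contains a drift of 5 dB per night, the drift-free SD is √(225 − 54.5) = 13.1 dB. Power is 90.6% (paired t), 94.2% (pairwise) and 96.5% (pooled).

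**Would the covariate screen rescue period?** If period were put through the P < 0.20 screen with the 15 dB effect present, it would be kept in 12% of trials at 3 dB per night and 36% at 5 dB when the screen ignores patient (assumed between-patient SD 10.6 dB). A repeated-measures screen would keep it in 24% and 54%.

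**Losses.** With three orders, each order carries the two-step night difference for exactly one contrast. Losing one patient from that order leaves a mean night difference of (4 + 4 − 6)/11 = 0.18; losing two leaves (4 + 4 − 4)/10 = 0.40. At 5 dB per night the bias is 0.9 or 2.0 dB.

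**The case against.** The strongest reply is that nothing here is invalid. With balanced orders the paired t-test is unbiased, its type I error does not exceed 5%, and it meets the stated power. The harm depends on a drift that the protocol does not give. Ten dB per night is 20 dB over the study, more than the target difference. Design features limit drift: a prior PSG night, a demonstration of the AAT, a fixed time after dosing and a fixed sleep stage. For a first-night shift of 5 dB, a period-adjusted pairwise contrast gains almost nothing. The remedies have costs too: the 9 df contrast loses 1 to 2 power points without drift, and the pooled model can be anti-conservative when variances differ. The protocol never says that period would go through the covariate screen. The bias needs drift, losses and imbalance together, and the budget in Section 2.10 is for 12 completers, which may mean replacement.

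Much of this stands. The size is unknown and may be small, the retention figures hold only if period is screened, and the missing margin is a separate matter that a period term does not cure. Three things remain. The protocol names the test, so the choice is not merely left to a later plan. Nothing in the text puts period in the primary contrast or guarantees it elsewhere. Replacing patients would not by itself restore balanced orders.

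**Conclusion.** The point holds. The named primary test leaves out the period structure that the design was built to balance. With orders intact the cost is precision, not bias: about 2 power points at 3 dB per night, 5 points at 5 dB (88% to 83%, half-width 9.3 to 10.4 dB), and a fall below the stated 70% only near 9 dB per night. If losses leave the orders unequal, a bias of 0.18 to 0.40 dB per dB of nightly drift is added for one loss, or two in the same order. These figures rest on an assumed linear drift, an SD of differences of 15 dB and a two-sided 5% level. The change should be made because it is cheap and protects against an effect of unknown size; the trial is not unsound without it. Confidence is medium, because the protocol gives no night effect.

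**What to change.** In Section 2.7, make the primary analysis one within-patient model with treatment and period as fixed effects and patient as a block or random effect. State that period is pre-specified and exempt from the P < 0.20 screen. Take all three contrasts (20 mg and 10 mg against placebo, and 20 mg against 10 mg) and their 95% intervals from this model. Keep the paired t-tests as a sensitivity analysis.

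Validity should not rest on equal variances. Either allow treatment-specific variances or use the period-adjusted pairwise contrasts. With assumed within-person SDs (placebo/10 mg/20 mg) of 10/5/10 or 10.6/10.6/21.2 dB, type I error for 20 mg against placebo in the equal-variance pooled model rose to 8.5% and 7.8%. The period-adjusted pairwise contrast stayed at 4.8% and 4.9%. The treatment-specific-variance model was not simulated at this sample size, so its small-sample behaviour should be checked before it is chosen.

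The cost is two sentences, with no extra patients, nights or data. Period takes two degrees of freedom. The pairwise version has 9 df instead of 11, loses 1 to 2 power points if there is no drift, and breaks even at about 3 dB per night.
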